- Visit 8 – Safety Follow Up: approximately 42 weeks after the initial investigational product administration, active study participants will complete a follow up visit at the clinic site.
- Visit 9 – End of Study, during this final visit (approximately 52 weeks after Week 0) a complete group of study assessments will be performed to evaluate the safety and efficacy of HB-adMSCs or Placebo administrations.

Clinical assessments of disease activity will take place during the following visits:

- Visit 1 – Screening
- Visit 2 – Infusion 1 (**Baseline**)
- Visit 4 – Infusion 3
- Visit 6 – Infusion 5
- Visit 8 – Follow Up
- Visit 9 – End of Study

Blood samples for safety assessments will be collected in as follows:

- Visit 1 – Screening: after informed consent has been obtained, blood samples should be collected from a vein of the study's participant arm, these lab results will help assess the subject's eligibility.
- Visit 2 – Infusion 1, (**Baseline**): safety laboratory samples will be collected from the study participant's vein to establish a baseline for comparison with the laboratory results obtained in subsequent visits.
- Visit 6 – Infusion 5: safety laboratory samples should be collected from a vein of the study's participant arm during this visit.

Visit 9 – End of Study: safety laboratory samples should be collected from a vein of the study's participant arm during this visit.

For study participants who do not complete the study trial, a safety follow-up visit will be scheduled as follows:

- For subjects who did not receive any of the investigational products and were eligible to participate in the trial, they will be invited to a safety follow-up visit, or Early termination visit (ETV) within 30 days after the last visit.
- For subjects who received at least one dose of the investigational product, they will be invited to a safety follow-up visit, approximately 30 days following that single treatment.
- For subjects who received more than one dose of the investigational product, they will be invited to a safety follow-up visit, approximately 30 days following the last treatment.

Withdrawal Criteria

In different situations, a study subject may withdraw from the study before the planned completion of the visits. One of these situations is mentioned below,

1. Voluntary withdrawal: subject doesn't want to continue receiving the investigational product.

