Unanticipated Problems Involving Risk to Subjects or Others

Any incident, experience, or outcome that meets all the following criteria:

- Unexpected in nature, severity, or frequency (i.e., not described in study-related documents such as the IRB-approved protocol or consent form, the investigators brochure, etc.)
- Related or possibly related to participation in the research (i.e., possibly related means there is a reasonable possibility that the incident experience, or outcome may have been caused by the procedures involved in the research.)
- Serious (as defined below) ***“Serious” is different than “severe” as reported in the CTC criteria that applies a grade to the AE.***

Adverse Event

An ***adverse event*** (AE) is any symptom, sign, illness, or experience that develops or worsens in severity during the study. Intercurrent illnesses or injuries should be regarded as adverse events. Abnormal results of diagnostic procedures are adverse events if the abnormality:

- results in study withdrawal
- is associated with a serious adverse event
- is associated with clinical signs or symptoms
- leads to additional treatment or to further diagnostic tests
- is considered by the investigator to be of clinical significance

Serious Adverse Event

Adverse events are classified as serious or non-serious. A ***serious adverse event*** is any AE that is:

- fatal
- life-threatening
- requires or prolongs hospital stay
- results in persistent or significant disability or incapacity
- a congenital anomaly or birth defect
- an important medical event

Important medical events are those that may not be immediately life threatening but are clearly of major clinical significance. They may jeopardize the subject and may require intervention to prevent one of the other serious outcomes noted above. For example, drug overdose or abuse, a seizure that did not result in in-patient hospitalization, or intensive treatment of bronchospasm in an emergency department would typically be considered serious.

All adverse events that do not meet any of the criteria for serious should be regarded as ***non-serious adverse events***.

Adverse Event Reporting Period

The study period during which adverse events must be reported is normally defined as the period from the initiation of any study procedures to the end of the study treatment follow-up. For this study, the study treatment follow-up is defined as approximately 20 weeks following the last administration of study treatment.

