

• To identify the safety of intravenous infusions of HB-adMSCs vs. Placebo in patients with Multiple Sclerosis as determined by changes in Patient Health Questionnaire (PHQ-9) (Time frame: Baseline to Week 52).

• To assess the safety of intravenous infusions of HB-adMSCs vs. Placebo in patients with Multiple Sclerosis as determined by the incidence of adverse events or serious adverse events (Time frame: Baseline to Week 52).

	

• Change from baseline at Week 52 in Patient Health Questionnaire (PHQ-9) scores following treatment with HB-adMSCs or Placebo

• Incidence of treatment-emergent Adverse Event (TEAEs) and serious Adverse Events (SAEs)

• Incidence and risk of AEs of special interest (serious or nonserious), including thromboembolic events, peripheral events defined as, thromboembolism of the extremities, also infections and hypersensitivities.

• Clinically significant changes in laboratory values, vital signs, weight, physical examination results and Multiple Sclerosis concomitant medications.

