## 2.2. Study Design

Overview of Study Design and Key Features	
	<pre> graph TD     Screening[Screening] --> Eligible{Eligible}     Eligible -- No --> ScreeningFailure[Screening Failure]     Eligible -- Yes --> Randomization[Randomization]     Randomization --> Week0[Week 0 (Baseline)]     Week0 --> Week4[Week 4 INF # 2]     Week4 --> Week8[Week 8 INF # 3]     Week8 --> Week16[Week 16 INF # 4]     Week16 --> Week24[Week 24 INF # 5]     Week24 --> Week32[Week 32 INF # 6]     Week32 --> Week42[Week 42 Follow Up]     Week42 --> Week52[Week 52 EOS]   </pre>
Design Features	
This study will be a randomized, double-blind, single center, phase 2 study to assess efficacy and safety of multiple HB-adMSCs vs. Placebo for the treatment of Multiple Sclerosis. The trial includes,
 
 
• A screening period of up to 4 weeks
 
• A 32-week treatment period while on randomized study treatment 
 
▪ Infusion 1 (Week 0), Infusion 2 (Week 4), Infusion 3 (Week 8), Infusion 4 (Week 16), Infusion 5 (Week 24) and Infusion 6 (Week 32)
 
 
 
• A safety Follow-up period of 20 weeks after the last investigational product administration. 
 
▪ Follow up at week 42 and end of study at Week 52
 
 
 
• 24 Subjects
 
• 2 Treatment groups 
 
▪ Group 1 → HB-adMSCs
 
▪ Group 2 → Placebo
 
 
 

Study Intervention	
 
• Active Product: HB- adMSCs (Hope Biosciences adipose derived mesenchymal stem cells) 
 
▪ Dose: 200 million
 
▪ Route: Intravenous
 
▪ Regimen: Weeks 0, 4, 8, 16, 24 and 32.
 
 
 
• Placebo: Saline Solution 0.9% 
 
▪ Dose: N/A
 
▪ Route: Intravenous
 
▪ Regimen: Weeks 0, 4, 8, 16, 24 and 32.
 
 
 
• Duration of administration 1 hour
 
• Study treatment details,
 

Overview of Study Design and Key Features		

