### **5.3.2.2. Adverse Events**

AEs will be coded using the most recent version of the Medical Dictionary for Regulatory Activities (MedDRA).

A treatment emergent adverse event (TEAE) is defined as an event that has onset date on or after the first day of exposure to infusion treatment and on or before the first safety follow up at week 42/early withdrawal date. Here the first day of exposure is defined as the first day of exposure to infusion treatment.

Treatment emergent Adverse events TEAEs are summarized descriptively, whereas non-TEAEs are presented in listings. TEAE data will be displayed in terms of the number of subjects with at least one event (N), percentage of subjects with at least one event (%) and the number of events (E).

Summaries of TEAEs and of serious AEs will be presented as an overview including all AEs, serious AEs, AEs by severity, AEs by relation to treatment, action to AEs and treatment advised, and outcome of AEs.

Furthermore, summary tables based on system organ class and preferred terms are made for:

- All TEAEs
- Serious AEs
- AEs leading to withdrawal of study
- Incidence and risk of AEs of special interest (serious or nonserious), including thromboembolic events, peripheral events defined as, thromboembolism of the extremities, also infections and hypersensitivities.

Individual adverse events will be listed.

The details of the planned displays are in programming specification document.

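### The SAP closes the treatment-emergent window at the Week 42 visit or an undefined early withdrawal date, but the adverse-event endpoints run to Week 52, so later-onset events drop out of the TEAE summaries

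*SAP*

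**What the plan says.** SAP 5.3.2.2 opens the treatment-emergent window with "an event that has onset date on or after the first day of exposure to infusion treatment" and closes it "on or before the first safety follow up at week 42/early withdrawal date". On reporting it says: "Treatment emergent Adverse events TEAEs are summarized descriptively, whereas non-TEAEs are presented in listings".

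The safety objective in SAP 2.1 is set "as determined by the incidence of adverse events or serious adverse events (Time frame: Baseline to Week 52"), and the first endpoint given for it is "Incidence of treatment-emergent Adverse Event (TEAEs) and serious Adverse Events (SAEs"). The protocol's Endpoints section lists the same incidence under both primary and secondary endpoints, each assessed from baseline to Week 52.

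On collection, the protocol's Adverse Event Reporting Period states that "the study treatment follow-up is defined as approximately 20 weeks following the last administration of study treatment". Its schedule of assessments has adverse events assessed at Visit 9 (Week 52), and the Visit 9 procedures ask for events since the previous visit, which is Week 42. For participants who leave early after more than one dose, "they will be invited to a safety follow-up visit, approximately 30 days following the last treatment".

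SAP 7.2.2 holds a second treatment-emergent rule. It marks events before the first dose as Y and events on or after it as N, and it has no end date.

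**The concern.** The endpoint has a 52-week time frame and the data are collected for 52 weeks, but the definition behind the TEAE tables stops at Week 42. The SAP gives no reason for the earlier cut, and nothing in the protocol calls for it.

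An event that starts after the Week 42 visit is recorded and then appears only in a listing. A listing gives no number of subjects, percentage or event count by arm, and incidence by arm is what the endpoint asks for. The TEAE table would therefore describe a shorter period than its stated time frame, with counts that are too low for that time frame if any events start late. With about 12 participants per arm, one participant is 1/12 = 8.3% of an arm, so a single late event can visibly change a row of the table.

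Two further uncertainties come with the cut: whether it also governs the serious and special-interest tables, and what date closes the window for someone who withdraws.

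**Working it through.** **Inputs.** Last infusion at Week 32 (SAP 2.2: "Infusion 5 (Week 24) and Infusion 6 (Week 32")). Follow-up visits at Weeks 42 and 52 and a 20-week safety follow-up (SAP 2.2). Time frame to Week 52 (SAP 2.1). 24 participants (SAP 2.2 and 6), about 12 per arm (protocol, Investigational Product Assignment).

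**The plan's own figure.** Follow-up after the last infusion = 52 − 32 = 20 weeks, which matches the stated 20 weeks.

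**What the cut leaves out, in nominal weeks.**
- Weeks after the cut: 52 − 42 = 10.
- Share of post-treatment follow-up: 10/20 = 50%.
- Share of the whole time frame: 10/52 = 19.2%.
- If all 24 complete: 24 × 10 = 240 of 24 × 52 = 1,248 participant-weeks.

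**Sensitivity to visit timing.** The window row of the schedule table is broken in the text available. Assuming ±7 days at each of Weeks 32, 42 and 52, the gap is 8 to 12 weeks, or 40% to 60% of follow-up.

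**Effect on what is reported.** SAP 5.3.2.2 reports subjects with at least one event (N and %) and the number of events (E). These respond differently to the cut. Assume, for illustration only, a constant event rate.
- Event counts: 10/52 = 19.2% are excluded, whatever the rate.
- Subjects with at least one event: if the 52-week probability is p, the 42-week probability is 1 − (1 − p)^(42/52).

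| Over 52 weeks | Over 42 weeks |
|---|---|
| 5% | 4.06% |
| 10% | 8.16% |
| 20% | 16.49% |
| 50% | 42.87% |
| 63% (mean 1 event per subject) | 55% |
| 95% (mean 3 events per subject) | 91% |

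The relative loss is close to 19% for rare events (1 − 4.06/5 = 18.8%) and falls to about 4% when nearly everyone has an event (1 − 91/95 = 4.2%). The documents give no event rate, so the table shows a range and not a forecast.

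**Early leavers.** The documents do not define the early withdrawal date. If it is the date of the decision to leave, events between that date and the safety visit about 30 days after the last treatment fall outside the window. If it is the date of that visit, they fall inside.

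**The two SAP definitions.** Correcting the reversed labels in SAP 7.2.2 would make every event on or after first dose treatment-emergent, with no end date, along with events whose date is missing or partial. That rule would count onset after Week 42, and SAP 5.3.2.2 would not. Editing either section alone leaves two definitions that can disagree.

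**The case against.** The strongest reply is that nothing is lost. Late events are collected and listed, a treatment-emergent window shorter than the collection period is not in itself an error, and the cut applies equally to both arms. The protocol never defines a TEAE, so the SAP's statement in 5.4 that there is no deviation from the protocol is not plainly false.

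Most of this stands. It does not answer the mismatch: the endpoint is incidence to Week 52, the tables stop at Week 42, and no reason is given.

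The reply does defeat several stronger readings that a reader might infer.
- **That late serious and special-interest events certainly vanish from the arm comparison.** Of the four tables by system organ class and preferred term in SAP 5.3.2.2, only the first is labelled as TEAEs. The tables for serious events, events leading to withdrawal, and special-interest events carry no such limit. The sentence sending non-TEAEs to listings points the other way. The text is ambiguous, so a serious event at Week 45 may or may not be tabulated.
- **That TEAE incidence is the only safety measure.** SAP 2.1 also lists SAEs, special-interest events, and changes in laboratory values, vital signs, weight, physical examination and MS concomitant medications.
- **That events found at the 30-day visit are certainly uncounted.** This depends on the undefined withdrawal date. Under the protocol's infusion stopping rules, a participant whose infusion is stopped for an adverse event is still followed, so may have no early withdrawal date at all.
- **That reported incidence falls by 19%.** That figure applies to event counts under a constant rate, and only approximately to the percentage of subjects when events are rare. All infusions and 24-hour calls fall by about Week 32, so ascertainment is denser early and a constant rate has no support in the documents.

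**Conclusion.** The mismatch holds. As written, SAP 5.3.2.2 leaves events with onset after the Week 42 visit out of the TEAE summaries, although the endpoint's time frame and the data collection both run to Week 52. The gap is nominally 10 of 20 post-treatment weeks and 10 of 52 weeks overall. This part rests only on the visit schedule and the definition.

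The consequences are less certain. Under an assumed constant rate about 19% of event counts would be excluded, while the effect on the percentage of subjects with at least one event depends on the rate. Late serious and special-interest events, and events in early leavers after withdrawal, may be left out, depending on readings the SAP does not settle. The documents do not show a bias between arms.

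This should be corrected before the safety tables are programmed. It does not threaten the data themselves, which are collected and listed either way.

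**What to change.** In SAP 5.3.2.2, define a TEAE as an event with onset on or after the first infusion and up to the Week 52 End of Study visit or, for participants who leave early, the last safety follow-up contact. That wording also removes the dependence on an undefined withdrawal date.

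Use the same definition and end date in SAP 7.2.2, with its Y and N labels corrected. State that the serious and special-interest tables use the same window.

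If the sponsor wants the shorter window, show onset up to Week 42 as an additional split, by arm.

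The cost is a few lines of SAP text in two sections and one date in the programming, with no new data and no change to study conduct. The downside for the sponsor is that TEAE counts may be slightly less favourable.

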#### **5.3.2.3. Clinical Laboratory data**

Laboratory evaluations will include the analyses of Biochemistry laboratory tests, Hematology laboratory tests and Urinalysis. The details of the planned displays are in programming specification document.

All laboratory parameters, including numerical urine analysis parameters will be summarized descriptively. Categorical urine analysis results will be summarized using count and percentage based on subjects.

Results of urine pregnancy test will be listed in individual subject data listings only.

Individual laboratory evaluations will be listed. In addition, a listing containing individual subject laboratory values outside the normal reference ranges will be provided.

Data recorded at unscheduled assessments will not be included in tables and figures but will be listed.

#### **5.3.3. Additional Safety Assessments**

The analyses of non-laboratory safety test results will include physical examination and vital signs.

Physical Examination and Vital signs will be summarized using count and percentage based on subjects. The vital signs based on visit and change from baseline will be summarized using descriptive statistics.

Individual Vital signs, Physical Examination evaluations will be listed.

The details of the planned displays are in programming specification document.

#### **5.4. Changes to Protocol Defined Analyses**

Analysis is planned as per protocol. No deviation from the planned protocol specified analysis.

### **6. SAMPLE SIZE DETERMINATION**

Sample size consists of up to 24 subjects who have been diagnosed with Relapsing Remitting Multiple Sclerosis.

### **7. SUPPORTING DOCUMENTATION**

#### **7.1. Appendix 1 Study Population Analyses**

Unless otherwise specified, the study population analyses will be based on the “Safety” population. Screen failures will be summarized or listed based on the “Screened” population. A summary of the number of participants in each of the participant level analysis set will be provided.

##### **7.1.1. Subject Disposition**

A summary of the number and percentage of subjects who completed the study as well as those who withdrawn from the study will be provided by treatment. Reason of study withdrawn will be summarized by treatment.

A summary of the study intervention status will be provided. This display will show the number and percentage of subjects who have completed the Week 52, as well as primary reasons for withdrawn.

The study analysis set will be summarized in the subject disposition table.

The details of the planned displays are in programming specification document.

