If an infusion is stopped for a subject due to an adverse event or serious adverse event, including but not limited to hypersensitivity reaction/anaphylaxis, no additional study treatment will be given to the study participant who develops the event. Although, the study participant will not receive the investigational product, he or she must be followed for safety purposes according to the protocol.

Study Stopping Rules

This Clinical Trial will stop if any of the following events are present:

1. Subject's Death.
2. Occurrence of any thromboembolic event during or after HB-adMSCs administrations (up to 72 hours).
3. Any cerebrovascular ischemia or seizure event occurring within 72 hours after any of the investigational product administrations.
4. Any Serious Adverse Events determined to be related to the following:

- When there is one CTCAE.v5 grade 4 or 5 AE, irrespective of attribution.
- Either any CTCAE Grade 2 adverse event that persists for more than two weeks, or any Grade 3 adverse event, that occurs within 72 hours after product administration.

Should the study participant discontinue study treatment he/she will be followed for safety according to the protocol safety monitoring plan. The study participant will receive follow up communication via phone calls and/or electronically to ascertain the outcome until resolved fully. All will be documented as per protocol.

All changes to the study stopping rules shall be reviewed by FDA. If the study is suspended for any reason, it will not be re-opened until FDA agrees. Regardless of whether the study is stopped or suspended all subjects will be followed to the EOS as per protocol.

Statistical Methods

Sample size consists of up to 24 subjects who have been diagnosed with Relapsing Remitting Multiple Sclerosis. All data collected from subjects who are enrolled and received the investigational product will be analyzed. The incidence of Adverse Events and Serious Adverse Events will be recorded and reported. Efficacy will be measured by improvement of subject's signs and symptoms associated with Multiple Sclerosis. Interim analysis of all safety and efficacy data may be performed at any time deemed appropriate by the Sponsor. Although, the subject's data may be analyzed at any time, a data analysis of all available data will be conducted when a least 10 subjects in each group have completed Week 24. Data may be analyzed for internal informational purposes, reports, presentations, and manuscripts.

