#### HB-adMSCs - Placebo

Pairwise t-test will be performed on the efficacy endpoints to test the difference between baseline and week 52 (EOS) as secondary analysis. Data for all the efficacy outcomes will be checked for normality (Shapiro-Wilk Test). When there is a larger deviation of data distribution from normality, appropriate non-parametric test will be used.

Additionally, RMA and ANCOVA in a Bayesian framework using a non-informative prior will be conducted to estimate the posterior distribution and to estimate the probability that the true treatment difference of change from baseline to Week 4, Week 8, Week 16, Week 24, Week 32, Week 42 and Week 52.

Study population analyses including analyses of subject disposition, demographic and baseline characteristics, medical history, prior and concomitant medications.

Disposition summary includes, subject screened, randomized and disposition at end of study – Week 52 along with reasons for withdrawals. Subjects in different analysis populations also will be presented.

The screen failure table includes total number of screened subjects and reasons. The percentage in the screen failure table will be calculated based on total number of screened subjects as denominator.

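### The SAP's intervention-status display counts Week 52 completion, so a participant taken off infusions for an AE but followed to Week 52 is shown as completing the intervention

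*SAP*

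**What the plan says.** SAP 7.1.1 plans two displays. The first is study status: "A summary of the number and percentage of subjects who completed the study as well as those who withdrawn from the study", by treatment, with reasons. The second is introduced as something different, "A summary of the study intervention status will be provided", and is then specified as follows: "This display will show the number and percentage of subjects who have completed the Week 52, as well as primary reasons for withdrawn". SAP 5.1.1 describes disposition at the same time point: "disposition at end of study – Week 52 along with reasons for withdrawals".

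SAP 2.2 separates treatment from follow-up. It gives "A 32-week treatment period while on randomized study treatment", with six infusions from Week 0 to Week 32, and then "Follow up at week 42 and end of study at Week 52".

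SAP 5.3.2.2 lists the SOC/PT tables: all TEAEs, serious AEs, "AEs leading to withdrawal of study", and AEs of special interest. None is keyed to stopping the infusions.

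The protocol's infusion stopping rules say that when an infusion is stopped for an AE, that participant receives no further study treatment, but "he or she must be followed for safety purposes according to the protocol".

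**The concern.** Being off the product and being off the study are different states, and the protocol expects some participants to be in the first without the second. The SAP reserves a display for intervention status but fills it with study status, and its only SOC/PT discontinuation table also concerns study status. Read literally, neither shows that an AE ended treatment in someone who stayed in follow-up.

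Safety is a stated objective, and AEs that end treatment are a main tolerability result by arm. There is also a link to the efficacy set, which SAP 4 restricts to participants who received all six infusions. The reasons for receiving fewer are tabulated nowhere for those who remain in the study, so a reader cannot see whether the causes of exclusion differ between arms.

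**Working it through.** The documents state no figure to reproduce. The check sets the definitions side by side and then sizes the miscount.

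**Time points.** Last planned infusion: Week 32. Completion point used in the display: Week 52. Gap: 52 − 32 = 20 weeks, all of it follow-up without product. Week 52 attendance therefore does not measure receipt of the intervention.

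**One participant traced through the plan.** Suppose the second infusion (Week 4) is stopped for an AE, no more product is given, and the participant is seen at Week 52.

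- Study completion (SAP 7.1.1, first display): completed. Correct.
- Intervention status (SAP 7.1.1, second display): completed. Wrong, because fewer than six infusions were received.
- SOC/PT table of AEs leading to study withdrawal (SAP 5.3.2.2): absent. Correct for its title, but no other SOC/PT table shows the stop.
- All-TEAE table and AE listing (SAP 5.3.2.2): the event is present.
- Exposure (SAP 5.3.2.1, stop date minus start date, divided by 7): about 28/7 = 4 weeks, against 224/7 = 32 weeks for a full course.
- Efficacy set (SAP 4): excluded, with no reason tabulated.

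The plan would thus report the same person as completing the intervention and as outside the set defined by all six infusions.

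**Size.** The protocol randomizes 24 participants 1:1, about 12 per arm. Let k be the number in an arm of 12 who were stopped for an AE and followed to Week 52, with everyone else completing. The display reads 12/12 = 100%. The share who received all infusions is (12 − k)/12.

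| k | Display | Received all six | Overstatement in arm (k/12) | Of all 24 (k/24) |
|---|---|---|---|---|
| 1 | 100% | 91.7% | 8.3 points | 4.2 points |
| 2 | 100% | 83.3% | 16.7 points | 8.3 points |
| 3 | 100% | 75.0% | 25.0 points | 12.5 points |

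The table of AEs leading to study withdrawal shows none of the k participants.

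**Likelihood.** This needs the per-participant rate p of AE-related stops and the proportion r of those stopped who reach Week 52. The documents give neither. For assumed p of 2%, 5%, 10% and 15%, the chance of at least one AE stop in an arm of 12 is 1 − (1 − p)^12 = 22%, 46%, 72% and 86%. These are chances of any stop. The chance of a miscount is 1 − (1 − pr)^12, which is zero if r = 0 and reaches those values only if r = 1. They are ceilings under assumed rates, not estimates.

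**The case against.** **The information is largely there.** The event appears by SOC/PT among all TEAEs and, if it is a hypersensitivity, infection or thromboembolic event, in the special-interest table. Individual AEs are listed, exposure would be visibly short, and analysis-set counts show how many lacked six infusions. The AE overview includes the action taken for AEs, where a stop may appear, although its categories are not defined. All of this stands. A reader might infer that the plan conceals AE-related stops or tabulates nothing but study withdrawals, and the documents do not support that. What is missing is an aggregate display of treatment completion with reasons, and a SOC/PT breakdown of the AEs that ended treatment.

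**Such participants may be recorded as withdrawals.** The protocol's Withdrawal Criteria treat not wanting further product as leaving the study. The early-termination text provides a safety visit about 30 days after the last infusion. The stopping rules speak of follow-up by phone or electronically, and the explicit statement about following everyone to end of study is tied to the study being stopped or suspended. Participants handled as study withdrawals would be counted correctly. This also stands and makes the point conditional. It also means that the same event could be classified in two ways, so these protocol sections need reconciling.

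**Display details are deferred to the programming specification.** It is not among the documents, so a suitable table may exist there. But SAP 7.1.1 is not silent on content: it gives an explicit definition that does not match the label.

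**Nothing inferential changes.** Agreed. The efficacy set is defined directly by infusions received, not by this display. A reader might infer that the primary comparison is altered by the mislabelling; it is not.

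**Conclusion.** The point holds as a fault in descriptive disposition and tolerability reporting. SAP 7.1.1 defines intervention status by a visit 20 weeks after the last planned infusion. A participant stopped for an AE and retained to Week 52 would therefore be shown as completing the intervention and would be missing from the only SOC/PT discontinuation table. Each one overstates completion by 8.3 percentage points in an arm of about 12.

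This rests on two assumptions: that the SAP wording is applied literally, and that at least one such participant stays in follow-up to Week 52 rather than being recorded as a study withdrawal. How often that would happen cannot be derived from the documents.

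**What to change.** 1. In SAP 7.1.1, define intervention status by infusions received: all six, or fewer than six with the number received and the primary reason for stopping product, by arm. Keep Week 52 completion as the separate study-completion display.
2. In SAP 5.3.2.2, add a SOC/PT table by arm of AEs leading to permanent stop of study infusions, derived from the AE action taken and the infusion records. Keep the study-withdrawal table under its present title.
3. Reconcile the protocol's Withdrawal Criteria, early-termination visits and stopping rules on whether a participant taken off product remains in the study, so that each case is classified in one way.

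Cost: revised SAP wording and one extra table. One item must be confirmed first. The protocol requires a recorded reason for withdrawal from the study, but does not say that a reason for stopping product is captured for someone who remains in it. If the CRF lacks that field, it has to be added or the reason taken from source documents.
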